2. EXTERNAL IRB REVIEW HISTORY*

N/A

3. PRIOR APPROVALS:

Conflict of Interest (COI):

All research staff with a COI to report have completed the necessary disclosure processes.

4. OBJECTIVES*

Aim 1: Draw upon the literature and a User Centered Design approach to collect data from content area experts, caregivers, and individuals with lived experience of perinatal depression, to iteratively develop the Text4Moms tool (tailored text messages, video content, and peer navigator dashboard).

Aim 2: Evaluate preliminary effect direction and magnitude of Text4Moms in a pilot randomized trial (Text4Moms vs educational texts; ratio 2:1) with 30 at-risk pregnant individuals not in an MDE. *Compared to participants randomized to the control condition, those in Text4Moms will:* **H1:** show target engagement through improvement in “self-efficacy” of $\geq d = 0.2$ that can protect against development of an MDE; **H2:** show greater decline in Edinburgh Postnatal Depression Scale (EPDS) scores of $\geq d = 0.2$, and items indicative of RDOC constructs of “loss” and “threat.”¹

Aim 3: Examine implementation outcomes by evaluating the usage, acceptability, and feasibility of Text4Moms and its components: **H3:** Participant ratings will average at least 68 on the System Usability Scale for the Text4Moms system and components. **H4:** >70% of patients will show engagement in Text4Moms by opening $\geq 80\%$ of text messages and clicking on $\geq 30\%$ of links to enhanced content. **H5:** $\geq 30\%$ of mothers will engage with the chat and endorse 4 out of 5 on its utility.

5. BACKGROUND*

5.A.1 Significance

Perinatal depression is common, impairing, and preventable. In the United States, ~14% of pregnant individuals experience an incident major or minor depressive episode, with a similar rate occurring postnatally.^{2,3} Depressive disorders always carry a high personal toll. However, during this pivotal time, depression is associated with risk of preterm birth⁴; can negatively affect the dyad through impaired maternal-child attachment⁵⁻⁷; can adversely affect infant development⁸; and decrease breastfeeding initiation/duration.^{9,10} Federal agencies and provider organizations emphasize the need to screen individuals for depression in pregnancy and after delivery.^{11,12} Additionally, the US Preventative Services Task Force (USPSTF) showed compelling evidence that counseling strategies can be deployed to *prevent* perinatal depression (pooled risk reduction (RR)=0.61 [95% CI, 0.47 to 0.78], k=17, n=3094, I²=39%).¹³

INVESTIGATOR STUDY PLAN - REQUIRED

At risk individuals benefit the most from preventative interventions although at-risk determinations vary in the literature. While the USPSTF reviewed preventative strategies for both individuals considered “at risk” and those not necessarily at risk, high risk groups show the greatest reduction in depressive symptoms after engagement in an intervention (RR=0.55; 95% CI, 0.44 to 0.68).¹³ A number of factors constitute risk including a past history of depression, especially perinatal depression¹⁴⁻¹⁸; genetic factors¹⁹⁻²¹; history of sexual abuse, early childhood abuse and intimate partner violence^{22,23}; stress and poor social support^{14,18,24-26}; low socioeconomic status¹⁴; undesired pregnancy²⁷; perinatal complications²⁸; certain demographic characteristics such as adolescence²⁶ and extant subsyndromal depressive symptoms.^{29,30} Measures designed to *predict* who will become depressed³¹⁻³³ do not perform substantially better than questionnaires that include demographic items and query current symptoms, most likely because of collinearity among domains.^{34,35} On the other hand, screening for existing depression is successful. A variety of approaches are used including screening and mood monitoring via mobile applications and text messaging.³⁶⁻³⁹ Systems most commonly use the Edinburgh Postnatal Depression Scale (EPDS)^{38,39} and the Patient Health Questionnaire-9 (PHQ-9)^{36,37} as screeners. The acceptability of tech-based screeners is high.^{37,38}

The most commonly used *criteria* to identify high risk individuals for participation in prevention trials was presence of depressive symptoms not meeting syndromal criteria. Although different questionnaires were employed in the various studies, the most frequent was the EPDS at a threshold score of 9.⁴⁰⁻⁴⁴ Several successful studies also included individuals with a history of depression as at high risk.⁴⁵⁻⁴⁸ This tracks with the strong signal in the literature placing this group at high likelihood of depression relapse.

Research Domain Criteria (RDOC) provide utility to further explore mechanisms related to preventative interventions. RDOC offers a model to understand and further explore the neurobiological systems involved in perinatal depression.⁴⁹ Depression falls into the negative valence domain with features of loss and threat (anxiety/fear).⁵⁰ Depression also falls within the positive valence system with (lack of) reward responding, i.e. anhedonia.^{1,50-52} An empiric study supported the notion that among *perinatal* individuals, the systems placing them at risk include the negative valence domains such as threat (anxiety/fear) and loss.⁵³ Indeed, these systems fit in well with the risk factors noted above that are associated with perinatal depression. These include past trauma or adverse events related to being mothered and childhood, role transitions that can be exciting but also entail loss and anxiety, social isolation and poverty that increase feelings of loneliness, anhedonia, loss and anxiety. Enhanced self-efficacy and a sense of mastery can help perinatal individuals navigate these challenges.

Interventions based on interpersonal therapy (IPT), and peer support are proven to be effective in decreasing the risk of perinatal depression. Interventions based upon IPT^{45,46,54,55} reduce risk of a depressive episode by 50% or more.¹³ The IPT-based intervention (Reach Out, Stand strong, Essentials for new mothers; ROSE) focuses on areas that place individuals at risk for perinatal depression including difficulties with social support, role transitions and life stressors.^{45,46,55} The paradigm on which ROSE is based focuses on interpersonal change processes to reduce stress, increase self-efficacy and ameliorate depressive symptoms.⁵⁶ This intervention was explicitly tested in pregnant minority individuals and showed significant benefit compared to enhanced usual care.⁵⁷ Broadly speaking, this intervention can provide a road map to enhance self-efficacy and enhance resilience to mitigate risk of depression.⁵⁸⁻⁶⁰ As well, IPT

INVESTIGATOR STUDY PLAN - REQUIRED

principles may enhance social support through better acceptance and management of the interpersonal challenge (i.e. through improved social skills).

Support provision is critical but does not need to be extensive or in person. Provision of peer support also reduces risk of an MDE, particularly among those at highest risk.^{40,43,61} One landmark study illustrating the utility of peer support for perinatal depression provided support via telephone²⁴ as well as email and text.⁴¹ This finding mirrors evidence from internet-delivered interventions for depression, anxiety, and substance use, suggesting additional therapeutic benefit from guided electronic interventions (those with some human contact or involvement, however brief) over unguided interventions (those with no human contact).⁶² Researchers hypothesize that strong social support increases self-efficacy⁶³⁻⁶⁵ and this results in decreased risk of depression⁶³; this was shown in a study that used peers.⁶⁵

Self-efficacy and coping are important targets for decreasing depression risk. Self efficacy, or the extent to which people view their ability to exert control over themselves and/or their environment, is linked to risk of depression through its effects on hope, optimism and effort. It is a critical component of mental health and strong theories link it to risk of depression.^{63,66-69} Not surprisingly, risk factors for depression, such as trauma and childhood adverse events, challenge one's sense of self-efficacy. Improved self-efficacy is also a key mediator between relationship challenges⁶³ and depressive symptoms as well as stressful life events⁷⁰, including those occurring in the perinatal period.^{65,71} Mastery is related to self-efficacy but adds an emphasis on the ability of the self to emphasize control over the meaning and emotional consequences of events.¹¹³ Strong coping skills decrease the risk of perinatal depression.⁷¹ They relate to RDOC by diminishing negative valence (loss or threat) and enhancing the appreciation of positive events (positive valence). Accordingly, we will evaluate whether the proposed TMI engages self-efficacy and mastery in order to protect against the onset of a major depressive episode (MDE). Self-efficacy scales for perinatal individuals focus on the postnatal period and self-assessments of parenting abilities and activities, which are hard to assess in pregnancy and before parenting starts (for primigravidas). However, general assessments of self-efficacy and mastery may provide an area to target for symptom improvement and development of resilience against an incident MDE.

Technology based interventions show promising results. Helping perinatal individuals obtain the treatment they need can be challenging⁷²; only ~20% of individuals meeting criteria for an MDE receive psychological treatment.⁷³ Technological approaches can improve the connection with mental health treatment by removing barriers of transportation, lowering cost, reducing stigma, and minimizing childcare needs. Digital Health interventions are a viable approach for *preventing* perinatal depression as well.⁷⁴⁻⁸³ In general, the majority of programs are web-based applications (apps) deployed on computers or mobile devices. Although such interventions are potentially powerful, most have not made it into wider use. Of the mental health apps widely available, there is a lack of expert input and testing.⁸⁴ Whether evidence based or not, apps are used infrequently, even after they are downloaded.^{85,86} Curated databases may help clinicians identify apps for their patients⁸⁷, but patients still need to actively seek them out, register, develop user names, passwords, and the user must have adequate internet access as well as appropriate devices.⁸⁸

Text messaging interventions (TMIs) may engage more perinatal individuals compared to mobile Health (mHealth) apps. TMIs have a number of advantages that can increase access to preventative interventions; they require active consent only once, and then allow repeated,

INVESTIGATOR STUDY PLAN - REQUIRED

proactive, and direct contact over extended periods of time. Texts allow participants to focus on the intervention content through a known user experience with minimum effort required. For example, texts can be read automatically when received and indeed, more than 90% of text messages are opened and read within a few minutes.⁸⁹ Text messages are also inexpensive to send and receive, **can be tailored, personalized and made interactive.**⁸⁸ In this way, TMIs can adopt some of the strong features seen in standard web-based programs yet avoid some of the issues that arise when using apps.

TMIs are proven to be effective and have a broad reach. TMIs are being deployed to support pregnant and postpartum individuals in a variety of domains. A national initiative, Text4Babies, was developed in 2010 “to promote healthy pregnancies and babies by the use of text messages.”⁹⁰ Text4Babies and other systems are acceptable to pregnant and postpartum individuals, including underserved populations.⁹⁰ TMIs have significant therapeutic effects on attitudes toward alcohol use in pregnancy, smoking in pregnancy, compliance with prenatal visits, taking prenatal vitamins and eating fruits and vegetables.⁹¹⁻⁹⁵

TMIs can be used as an adjunct to ongoing treatment with clinicians for depressed individuals. Above we note the feasibility and success of screening via text messaging^{36,96,97}, which can identify individuals who need clinician-delivered treatment. As well, TMIs can be used as an *adjunct* to help depressed, perinatal individuals and were used in conjunction with nurses making home visits to perinatal women.⁹⁸ Indeed, a TMI designed to prevent depression may require minimal modification to be used as an adjunct to depression treatment in perinatal individuals, although that is not the focus of this application. For example, additional encouragement for managing role transitions and developing a support network can be beneficial for both individuals at risk and individuals in an MDE.

TMIs enhance self-efficacy. Non-enhanced text messages were used as a postnatal educational and peer support intervention for first time mothers with the goal of increasing parenting self-efficacy and decreasing postpartum depressive and anxiety symptoms.⁶⁴ In the initial pilot study, first time mothers were provided education through a TMI that delivered messages twice daily for 2 weeks and then daily for one month. The program, which was developed with expert and end-user (mothers) input, showed improvements in parenting self-efficacy.⁹⁹ A developer of this intervention is a consultant on the proposed project.

Design features to consider with mobile interventions. As work in this field matures, we can now appreciate that a number of components optimize design features of mobile interventions. Understanding and empathizing with the needs of the end-user (patient) is important for designing engaging mHealth interventions, including TMIs. It is clear that participant input can enhance engagement. User centered design (UCD) approaches enhance one’s ability to operationalize end-user input. UCD incorporates the needs, preferences, and limitations of end users into all phases of product development and implementation.^{100,101} In practice, UCD assesses these areas using repeated, mixed quantitative and qualitative measures to guide the design process. This approach allows for iterative refinement and product improvement through direct user input to increase the chance that systems work well in the native environment.¹⁰²⁻¹⁰⁴ UCD can be applied to the development of TMIs to enhance content for the individuals who will ultimately be recipients of texts.

Other features important to health app development include accessibility, privacy/security, clinical foundation, and interoperability.⁸⁷ Compared to web-based apps, TMIs may have less

INVESTIGATOR STUDY PLAN - REQUIRED

privacy and text messages need to be developed with that in mind by avoiding highly sensitive or incriminating content; but text messages can include links to content such as videos and live chat that can be provided with a high level of security.

Mobile health interventions focused on screening and prevention of perinatal depression are needed.

Despite the proven potential of mHealth interventions in perinatal depression treatment, what is needed is an *accessible* system to identify risk among perinatal individuals and

provide an intervention to *prevent* an MDE. This is particularly important for individuals from diverse racial and socio-economic backgrounds who may have few resources to care. In this application, we propose to apply UCD principles to:

- finalize and deploy a brief measure to screen pregnant individuals for an MDE and depression risk
- develop a subsequent set of one-way, tailored text messages based upon elements from preventative IPT interventions to improve self-efficacy and decrease the likelihood of perinatal depression
- provide peer support through secure chat functionality that will augment intervention elements to enhance social support for pregnant individuals at risk of depression.

[figure not shown]
5.B. Preliminary Studies

5.B.1. Depressive symptoms prior to an MDE. In the Yale Pink and Blue Study, we enrolled 2,654 pregnant individuals who had one of the following: were depressed, had a history of depression, were undergoing antidepressant treatment, or none of the above. Individuals were enrolled prior to 16 completed weeks gestation and were followed until 2 months post-delivery. We screened for depression with the EPDS and conducted diagnostic interviews with the Composite International Diagnostic Interview. We evaluated symptoms people experienced *before* an *incident* MDE (n=51) either in the 2nd or 3rd trimester. Figure 1 shows substantial distress with > 50% endorsing crying, feeling sad or miserable, overwhelmed, or anxious (scores of 2 or 3); fortunately, suicidal thoughts were low.

5.B.2. Screening for depression. [name] has been part of an international coalition to evaluate the psychometric properties of the EPDS in relation to diagnostic interviews. We contributed data from the Pink and Blue study. Results from 15,557 participants in 58 studies, including 2,059 individuals with an MDE indicated an optimal cutoff on the EPDS of 11.¹⁰⁵ This suggests that an EPDS score of 9 is likely to detect individuals at risk, but not in an episode of an MDE. The proposed study will also use CAT-MH for diagnostic information.

5.B.3. Social support and depression in pregnancy. My team evaluated the intersection between an MDE in pregnancy, pregnancy timing/wantedness and social support. Secondary analyses of our Pink and Blue data showed that individuals who said their pregnancy was poorly timed were 3.5 times more likely to be in an MDE⁹⁴; additionally, individuals who indicated that

Figure 1: EPDS Items Before Onset of MDE

INVESTIGATOR STUDY PLAN - REQUIRED

their pregnancy was poorly timed were nearly twice as likely to score in the bottom quartile of a social support measure. In a follow-up, cross sectional study of 161 individuals seeking pregnancy testing or termination, over one half of the cohort indicated low social support; unplanned pregnancies and depression were both associated with low social support.¹⁰⁶ This speaks to the role of social support in pregnancy and the possibility that peer support may mitigate risk of an MDE.

5.B.4. Computer vs. therapist-delivered screening and brief intervention for individuals seeking reproductive health care. [name] was corresponding co-PI of a recently completed NIDA-funded trial comparing person-delivered to a CIAS-based brief intervention for substance use among individuals seeking reproductive health services. Drs. [name] and [name] were co-Investigators in this study. Over a six-month follow-up, results of that trial show significant reductions in use of the primary substance for individuals in ob-gyn settings assigned to either the therapist-delivered or computer-delivered motivationally-based brief intervention, vs. an enhanced services condition.¹⁰⁷ Although small, effect sizes were more than sufficient to support a public health impact (e.g., 0.30 at 3 months and 0.17 at 6 months for the computerized intervention vs 0.22 and .06, respectively, for the therapist-delivered condition), particularly given the relative ease of implementation and low cost of technology delivered approach.

5.B.5. Integration of technology into prenatal care settings as part of usual care. [name] is currently leading a project implementing technology-based screening and brief intervention for behavioral health risks in prenatal care settings throughout Michigan. This project implements a mobile app that screens for a range of behavioral health risks including depression, provides a brief motivational intervention, and facilitates connection to other services. The app has been successfully integrated into ongoing clinical care at sites throughout Michigan, without provision of any additional funding for the sites, and without any study team involvement in the day-to-day integration of the technology. To date, over 5,000 pregnant patients have been successfully screened with high ratings for acceptability, high disclosure rates, and high rates of motivational intervention completion.

6. INCLUSION AND EXCLUSION CRITERIA*

Participants will be 40 individuals (10 in the pre-pilot and 30 in the pilot study) who are pregnant and at risk of, but not in a major depressive episode (MDE).

Inclusion/Exclusion Criteria for Participants:

- English speaking (it will be important to make this available in other languages eventually but for this preliminary work, translation processes and testing are not compatible with this scope of work and budget limits)
- “At risk” as determined by an Edinburgh Postnatal Depression Scale score of at least 9, or an average score >3 on the 6-item Medical Outcomes Social Support Survey or history of depression in pregnancy or postpartum depression
- At least age 16; we allow individuals who are as young as 16 because this is a high-risk group for perinatal depression and information on preventative interventions from this group is important
- Are willing and able to provide informed consent

INVESTIGATOR STUDY PLAN - REQUIRED

- Are not in a major depressive episode
- Do not have panic disorder or substance use disorder
- Are not planning on terminating pregnancy
- Are willing to use a smart phone to receive texts
- Are not currently in behavioral health care treatment
- Are not blind; the text messaging intervention requires that the patient can see
- Are not permanently living in an institutional setting; many in institutional settings will either lack capacity or constitute a vulnerable research group (e.g., prisoners)

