10. STUDY ENDPOINTS*

Outcome Measures:

- The Edinburgh Postnatal Depression Scale (EPDS) is a well validated¹⁰⁸, widely deployed, 10-item scale designed specifically for use with pregnant and postpartum individuals to measure depressive symptoms^{109,110}; a cutoff of 13 is the most specific to identify individuals who likely have an MDE.¹¹¹ This will be used to screen for depressive symptoms and as an outcome measure.
- The CAT-MH including the CAT-DI¹¹² is a computerized adaptive test that draws from an item bank of 452 items; individuals typically need to answer 12 items to render an accurate diagnosis of an MDE. The CAT DI module has a sensitivity of 0.92 and specificity of 0.88 when compared to the Structured Clinical Interview for DSM-IV. The CAT-MH is integrated into CIAS 3.0, allowing for seamless integration with other assessments. This will determine who has depression and needs intervention at the outset of the study (exclusion criteria) and will be used as an outcome measure to determine if the intervention decreased the risk of an MDE or anxiety disorder.
- The General Self Efficacy Scale (GSE scale)⁶⁸ has 10 items scored from 1-4 that measures an individual's belief that she can respond to novel or challenging situations. It takes ~2-4 minutes to complete, has a Chronbach's alpha of 0.82-0.93 and in individuals, is a single factor and correlated highly with self esteem and optimism. This is a target of the intervention that is putatively linked with depression risk. We evaluate whether the TMI changes self-efficacy and hence risk of an MDE.
- The Pearlin Mastery Scale (PMS)¹¹³ has 7 items that are scaled 1-4 (1= strongly disagree to 4= strongly agree) with a range of 7-28, and low scores indicating low mastery (Chronbach's

INVESTIGATOR STUDY PLAN - REQUIRED

alpha=0.78). This is also a target of the intervention and may be associated with lower risk of worsening depression.

- System Usability Scale¹¹⁴ has 10 items and is scored 1-5 (strongly agree to strongly disagree). Scores are summed and multiplied by 2.5. A score of greater than 68 is considered above average. This is a measure of acceptability that bears on ability to implement the system.

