randomization and the intervention timeline will be shortened. The pre-pilot participants will be either before 16 weeks or in the end of their third trimester of pregnancy and will participate for 4 weeks in order to capture various stages of pregnancy and the postpartum period. We will stagger recruitment and have 2 groups of 5 participants. The first group will start the pre-pilot at time T1, and the second group starts at time T1+1 month. This will allow us time to collect feedback after 2 weeks from group 1 and make adjustments (if any) needed to improve the intervention for the second group. The pre-pilot is important since it will allow us to evaluate the usability issues that can come up only after repeated use in the users' native environment, allowing us to address these issues before proceeding to a feasibility pilot. We will also be able to pre-pilot the peer mentor chat support. This step will confirm that all major issues related to use and usability are resolved before going into the pilot, which entails a 2-month intervention and 3 months follow up. Based on the feedback, which will focus on the points covered in PGG meetings, usability of the technology and acceptability of the intervention, we will make a final set of refinements to the multimodal intervention and move to a pilot study.

Aim 2 & 3: Evaluate preliminary efficacy, mechanisms, and implementation of Text4Moms in a pilot randomized trial.

Inclusion/Exclusion Criteria. We realize that the sample size for the pilot is small and will seek to recruit a cohort that is racially, ethnically, and socioeconomically diverse. Individuals will be eligible if they are: a) "at risk" as determined by: an EPDS¹⁰⁸ score of at least 9, or an average score >3 on the 6-item Medical Outcomes Social Support Survey (MOS)¹²⁰, and/or history of an MDE in pregnancy or postpartum depression;^{55,121} b) at least age 16; c) willing and able to provide informed consent. We allow individuals who are as young as 16 because this is a high-risk group for perinatal depression and information on preventative interventions from this group is important. Pregnancy confers "emancipated" status in Massachusetts, so these adolescents will be able to provide consent for participation. Pregnant individuals who are younger than 16 are uncommon in our setting.

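### The social-support route into the at-risk group has no stated range or direction and, on its plain reading, selects well-supported people instead of poorly supported ones

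*Combined protocol and SAP*

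**What the plan says.** Section 6 defines at risk by three alternatives: an EPDS of 9 or more, a past perinatal depression, "or an average score >3 on the 6-item Medical Outcomes Social Support Survey". The inclusion paragraph for Aims 2 and 3 in section 11 carries the same social-support rule. The alternatives are joined by 'or' (with 'and/or' before the history route in section 11), so the survey can qualify someone by itself. Section 6 applies the definition to all 40 participants, 10 in the pre-pilot and 30 in the pilot.

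The background explains why support matters. Section 5.A.1 lists "stress and poor social support" among the risk factors and later adds "social isolation and poverty that increase feelings of loneliness, anhedonia, loss and anxiety". On the protective side it says: "Researchers hypothesize that strong social support increases self-efficacy". Section 5.B.3 reports that women with poorly timed pregnancies were "nearly twice as likely to score in the bottom quartile of a social support measure", and that "unplanned pregnancies and depression were both associated with low social support".

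The assessment table in section 11 schedules the survey at baseline and 8 weeks. The scale descriptions in sections 10 and 11 have no entry for it. For the Pearlin Mastery Scale, by contrast, section 10 gives both range and direction: "with a range of 7-28, and low scores indicating low mastery".

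**The concern.** A survey named for social support would ordinarily be scored so that a higher average means more support. A rule that admits people above 3 then picks the better-supported end, while the rationale is about people with little support. Nothing in the documents argues for recruiting well-supported people, so this does not read as a deliberate choice.

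What is at stake is who the pilot represents. Aim 2 concerns pregnant individuals at risk of a major depressive episode, and section 5.A.1 says that people at risk gain most from prevention. Section 24 has eligibility collected through a REDCap survey, where an inequality programmed as written would be applied literally. Enrolment errors of this kind cannot be undone after randomisation.

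**Working it through.** **The cut-off itself.** The value 3 is given without derivation, so there is no figure behind it to reproduce. The check compares the texts.

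| Item | Where | Direction |
|---|---|---|
| Poor support is a risk factor | 5.A.1 | low = risk |
| Isolation is among the risk factors | 5.A.1 | low = risk |
| Strong support raises self-efficacy and so lowers depression risk | 5.A.1 | high = protective |
| Bottom quartile of a support measure (unnamed) is the unfavourable end | 5.B.3 | low = risk |
| Depression goes with low support | 5.B.3 | low = risk |
| Average above 3 on the support survey qualifies as at risk | 6 and 11 | high = risk, if high means more support |

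The first five rows agree. The sixth agrees with them only if the survey is scored so that a high value means little support, which no section says.

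**Who is affected, if high means more support.**
- EPDS below 9, no perinatal depression history, average above 3: admitted as at risk.
- EPDS below 9, no history, average of 3 or less: not admitted, although low support is the stated risk.
- EPDS of 9 or more, or a positive history: the at-risk test is met whatever the support score.

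Only the first two groups are misclassified. The other entry criteria apply throughout.

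**Weight of one person.** Each pilot participant admitted by this route alone is 1/30 = 3.3% of the pilot; 1/20 = 5% if in the Text4Moms arm, 1/10 = 10% if in the control arm. How many there would be cannot be computed from the documents.

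**How far direction matters (illustration only).** Assume an item average from 1 to 5, higher meaning more support, roughly normal with SD 0.8 to 1.0. None of this is in the documents. The share above 3 is 1 − Φ((3 − mean)/SD).
- Mean 2.5: 27% to 31% pass; 69% to 73% do not.
- Mean 3.5: 69% to 73% pass; the 27% to 31% with least support do not.
- Mean 4.0: 84% to 89% pass; the 11% to 16% with least support do not.

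These are shares passing this one rule among people screened, not shares of enrollees.

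**Power.** Section 13 states 80% power for d > 1.1 with 20 versus 10 and two-sided alpha 0.05.
- Normal approximation at d = 1.1: 1.1/√(1/20 + 1/10) = 2.840; 2.840 − 1.960 = 0.880; Φ(0.880) = 0.811.
- Two-sample t-test: power 0.783 at d = 1.1, and 80% power at d = 1.12.

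The stated figure is reproduced closely. It depends on the arm sizes and d, not on which way the criterion points.

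**The case against.** The strongest reply is that the reversal is inferred. The documents do not give the scoring, and the support measure in section 5.B.3 is unnamed, so it says nothing about how this survey is scored. In section 6 the rule stands beside an EPDS threshold where higher is worse, so above 3 might have been meant as the risk end. Section 10 describes the System Usability Scale as running from agreement at 1 to disagreement at 5; a support survey anchored in that way would score higher for less support. This part stands: the direction is undetermined, and the finding has to be conditional. None of these analogies, however, shows that this survey is reverse-scored.

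It is also fair that other scales lack detail. The EPDS has no stated range and the General Self Efficacy Scale no explicit direction, and section 13 does not analyse the support survey as an outcome. But an eligibility cut-off needs its direction known, and the EPDS threshold already agrees with the rationale.

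The screening form is still to be developed under Aim 1. That leaves room to correct it but does not alter the written criterion. Finally, the rule is applied before randomisation to everyone, so it does not bias the comparison between arms. That is right; the harm is to the population studied.

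**Conclusion.** The concern holds. It is certain that the survey's range, direction and cut-off source are missing. That the rule is reversed is an inference, held with medium confidence, and rests on a higher score meaning more support. On that reading the criterion contradicts the protocol's own rationale and would bring people into the pilot who are outside the Aim 2 population, while shutting out those whose only risk factor is low support.

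The number affected is unknown; the per-person weight is 3.3% of the pilot and up to 10% of an arm. Power and between-arm validity are not affected. Under either scoring the text needs an edit before enrolment, so this must be fixed.

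**What to change.** Before enrolment, reconcile the criterion in sections 6 and 11 with the rationale in sections 5.A.1 and 5.B.3, so that it selects the low-support end in both sections and in the REDCap eligibility logic. Beside the cut-off, state the survey's item range, its scoring direction and the source of the threshold; the team should confirm the exact value from the instrument's scoring. If the items are reverse-scored so that above 3 already means low support, keep the inequality and say so there.

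The edit is a change of wording in two sections, a scoring statement and one branch of the eligibility survey. The possible downside is a smaller eligible pool, by an amount the documents do not give. Section 25 assumes 200 screens for 40 enrollees, a yield of 40/200 = 20%. As an assumption only, if the yield fell to 15% or 10%, the screens needed would be 40/0.15 ≈ 267 or 40/0.10 = 400. That is 67 to 200 more, or $1,340 to $4,000 at the planned $20 each.
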